#### 8.4. Data Sources

This study relies on a secondary use of existing and available data in patient registers and patient charts in Finland. The data will be gathered from hospital patient information systems. All data in this study is collected from these patient information systems and made available in aggregated form for data-analysis.

#### 8.5. Study Size

This study is an observational study designed to provide mainly descriptive summary information. There are no hypotheses in the study. Hence sample size calculations are not applicable. The objective is to include all patients that have used to facitinib in UC in Finland. Estimated number of observations is 100-150 subjects to the timing on the data collection.

#### 8.6. Data Management

This study protocol will be evaluated and approved by the Finnish Health and Social Data Permit Authority Findata before any activity starts. Findata will issue permits and deliver the data for this study. Based on the protocol the clinical research organization (CRO) Medaffcon will design an eDMT form which will be provided to Findata. A predefined list of data miners will be submitted to Findata. eDMT form will be provided to data miners by Findata.

Each data miner will have access to a set of patient charts to collect the requested data using protected eDMTs. The eDMT is created and maintained by Granitics Oy. In each hospital district (register holder) the assigned data miner will transfer completed eDMT forms to Findata. Findata will provide the pseudonymized pooled data into a secure analysis environment, maintained by the same authority in a csv, xlsx or comparable format (not eDMT-format). Only a preassigned biostatistician from Medaffcon has access to this multifactor identification protected remote server, and only aggregate-level data can be extracted. Thus, individual patients cannot be identified from this data set.

Medaffcon will analyze the data using the statistical software R (version 3.6.1 or higher). Only aggregate results can be extracted from the Findata analysis environment and be available for evaluation for sponsor. Data will be stored at Findata. Medaffcon will be the study register holder, and analyses will be performed according to the SAP by Medaffcon and Pfizer.

Internal validity will be assured by consulting Finnish clinical experts on data integrity, clinical relevance, and plausibility of the results.

All results of this study will be presented in aggregate level data only, no individual level data can be reported. Any patient groups of less than 5 patients cannot be exported from Findata servers. This means that eg, if two patients smoke, it will be reported as "<5 patients smoke".

#### 8.7. Data Analysis

Detailed methodology for summary and statistical analyses of data collected in this study will be documented in a SAP, which will be dated, filed, and maintained by the sponsor. The SAP may modify the plans outlined in the protocol; any major modifications of primary endpoint definitions or their analyses would be reflected in a protocol amendment.

All analysis will be performed by Medaffcon. In short, patients will be described at baseline using appropriate summary statistics.

All analyses are descriptive of nature, and descriptive statistics and/or illustrations will be reported.

Persistence of treatment will be assessed using time-to-event models (namely Kaplan-Meier fit and/or Cox proportional hazards model). Changes in treatment outcomes (vs. baseline) will be assessed using repeated measures longitudinal models. Baseline data may be used as covariates in the models where feasible and appropriate.

All p-values are descriptive in nature, and there are no *a priori* hypotheses to be tested. P-values lower than 0.05 will be considered statistically significant. All statistical tests will be considered hypothesis generating, and any significant results should be validated later.

Statistical interpretation of the results will be validated by Medaffcon statisticians/Data Scientists with relevant degree.

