6 HANDLING OF MISSING VALUES

No imputation for missing values will be performed. Proportion of missing values will be reported where appropriate.

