7 STATISTICAL METHODOLOGY AND STATISTICAL ANALYSES

7.1 STATISTICAL METHODS

General:

Means, medians, and standard deviations, and 25% and 75% quartiles will be provided for continuous variables when performing descriptive analysis of continuous data. Numbers and percentages will be provided for dichotomous and polychotomous variables when performing descriptive analysis of categorical data.

Serial measures collected will be handled by "carry forward imputation", i.e. the latest value will be assumed unchanged until otherwise proven. Thus for each timepoint, the latest available measure will be used. Patients will be censored from the study post the last available contact/data entry. Missing values will not be imputed.

An unadjusted Kaplan Meier curve will be drawn to illustrate time-to-event and to estimate medians for time-to-event outcomes.

All data analysis will be executed using R, a language and environment for statistical computing and graphics, version 4.0.3 or later in Rstudio environment.

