Select only patients that were on remission/steroid free remission at the timepoints. For each patient, define the fulfilment of the remission/response criteria as Yes/No based on the latest available data (at each timepoint 16, 24 and 52 weeks). Report the proportion of patients on fulfilling the remission criteria, not censored at each timepoint.

Secondary objective l:

For each available Mayo score (full or partial), estimate the absolute delta change from baseline value. For each timepoint (week 8, 16, 24 and 52), report the summary statistics (mean, median, sd, 25%Q and 75%Q) of delta change, among patients not censored at each timepoint.

Secondary objective p:

Perform analyses described in secondary objective b and c, stratified by the extent of colonic involvement

Secondary objective q:

For each patient, define the corticosteroid tapering as Yes/No based on the latest available data (at each timepoint 8, 16, 24 and 52 weeks). Additionally, define the tapering rates and doses based on latest available data.

For each timepoint (week 8, 16, 24 and 52), report the proportion of patients that had corticosteroid tapered, among patients not censored at each timepoint. Additionally,

report summary statistics (mean, median, sd, 25%Q and 75%Q) of tapering rates and doses among patients that had corticosteroids tapered.

Secondary objectives r and s:

For each patient, define the fulfilment of the improvement criteria as Yes/No based on the latest available data (at each timepoint 8, 16, 24 and 52 weeks). Additionally, estimate the absolute delta change per baseline value

Report the proportion of patients on fulfilling the response/remission criteria, report the summary statistics (mean, median, sd, 25%Q and 75%Q) of delta change, among patients not censored at each timepoint.

Secondary objectives t-z:

For each subsequent laboratory measure, define "normal-level" as Yes/No variable. Additionally, estimate the absolute delta change per baseline value. For each timepoint (week 8, 16, 24 and 52), report the proportion of patients on fulfilling the "normal-level" criteria and summary statistics (mean, median, sd, 25%Q and 75%Q) of delta change, among patients not censored at each timepoint.

Secondary objective aa:

Report the proportion of patients that received extended induction

Secondary objective bb:

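### The SAP omits, without saying so, the protocol's longitudinal models for change from baseline and summarises latest-available values of unlimited age, while also ruling out imputation

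*Protocol*

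**What the plan says.** Protocol section 8.7 commits to a method for change: "Changes in treatment outcomes (vs. baseline) will be assessed using repeated measures longitudinal models". It adds that "Baseline data may be used as covariates in the models where feasible and appropriate", but names no outcomes, time coding or covariance structure. The same section says "All analyses are descriptive of nature, and descriptive statistics and/or illustrations will be reported" and "The SAP may modify the plans outlined in the protocol". It reserves formal amendment for the primary endpoint: "any major modifications of primary endpoint definitions or their analyses would be reflected in a protocol amendment".

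The SAP handles change differently. For objective l, section 7.2 says "For each available Mayo score (full or partial), estimate the absolute delta change from baseline value" and then asks for mean, median, SD and quartiles at each week among patients not yet censored. Objectives h, r, s and t-z follow the same pattern. Where Table 3 shows a change, it shows mean ± SD with no confidence interval.

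On serial measurements, SAP section 7.1 says that "for each timepoint, the latest available measure will be used", treating the value as unchanged until a new one appears, and censors patients after their last contact. SAP section 6 says "No imputation for missing values will be performed", and the paragraph in 7.1 that prescribes carrying forward also ends by ruling out imputation.

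SAP section 2.2 adds notes to objectives b/c, c/e and q where it departs from the protocol or doubts it. It has no note on the missing longitudinal models.

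**The concern.** Two problems meet here. First, a reader of the protocol expects model-based estimates of change, and a reader of the SAP finds raw deltas with no explanation. Protocol section 8.8 logs deviations from the SAP, so a SAP that departs from the protocol may not be picked up there.

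Second, the replacement depends on a rule that the SAP both states and denies. Two analysts could produce different week-52 tables from the same data, one carrying values forward and one not.

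The rule matters in this study because protocol section 8.9 expects incomplete data, with score components missing in some hospitals and some endpoints unavailable at some timepoints. Neither document sets a visit window or a maximum age for a carried value. Read literally, a week-8 score can stand as the week-52 score, and a baseline value with nothing after it can count as zero change. Censoring is at last contact and not at stopping treatment, so a patient who stops but is still seen can carry an on-treatment score forward. Table 3 has one row for N per week rather than one per outcome, so the number actually measured may never appear.

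**Working it through.** **The texts side by side.** The documents give no figure for this point, so there is nothing to reproduce.

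| Question | Protocol 8.7 | SAP |
|---|---|---|
| Method for change | Repeated-measures models | Delta summaries (7.2) |
| Reason for the switch | n/a | None given |
| Missing visit | Not stated | Latest value used (7.1); no imputation (6 and 7.1) |
| Age limit or visit window | None | None |

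**What carrying forward does.** If share w(k) of the week-52 values is carried from visit k, and missingness is unrelated to the score, then

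bias in mean change = Σ w(k) × [mean(k) − mean(week 52)].

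Negative bias means improvement is overstated. The sign depends on the course of the score after visit k.

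**Worked case (assumed inputs, not in the documents).** Each post-baseline visit is missing with probability 0.4 and nobody is lost. The carried shares at week 52 are 0.4 × 0.6 = 0.24 from week 24, 0.4² × 0.6 = 0.096 from week 16, 0.4³ × 0.6 = 0.0384 from week 8, and 0.4⁴ = 0.0256 from baseline.

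- Flat course, means 6/3/3/3/3 at weeks 0/8/16/24/52: 0.0256 × 3 = +0.08.
- Continuing improvement, 6/4/3.3/2.8/2.3: 0.24 × 0.5 + 0.096 × 1.0 + 0.0384 × 1.7 + 0.0256 × 3.7 = 0.120 + 0.096 + 0.065 + 0.095 = +0.38.
- Later loss of response, 6/3/3/3.3/3.8: 0.24 × (−0.5) + 0.096 × (−0.8) + 0.0384 × (−0.8) + 0.0256 × 2.2 = −0.120 − 0.077 − 0.031 + 0.056 = −0.17.

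**Simulation on the same courses.** It used 125 patients (within the protocol's 100-150) and 150 runs per scenario. Assumed: a partial-Mayo-like score with SD 1.8 at baseline and 2.2 later; correlation about 0.66 between adjacent visits; 0, 20 or 40% of visits missing; and either no loss or about 10% loss per interval after week 8, more likely after a worse score. The model was an unstructured multivariate-normal likelihood. The table gives the range of week-52 bias over the missingness and loss settings.

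| Course | True change | SAP rule | Observed values only | Longitudinal model |
|---|---|---|---|---|
| Flat | −3.0 | −0.04 to +0.08 | −0.04 to +0.01 | −0.03 to +0.02 |
| Improving | −3.7 | −0.08 to +0.39 | −0.08 to +0.03 | −0.07 to +0.03 |
| Later loss | −2.2 | −0.22 to +0.02 | −0.07 to +0.02 | −0.05 to +0.02 |

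Monte Carlo error is about 0.25/√150 = 0.02. Most of the error comes from the carrying itself, since plain observed-value summaries do nearly as well as the model here. What the model adds is a confidence interval and some protection when loss depends on earlier scores.

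**The case against.** The strongest reply is that the protocol allows this. Section 8.7 lets the SAP change the plan and asks for an amendment only for the primary endpoint. The primary objective is baseline characterisation, and every change-from-baseline outcome is secondary. The study is declared descriptive, and delta summaries are descriptive. That stands: a reader might infer a protocol breach, and the documents do not support one. What remains is that the change is neither declared nor explained, although other departures are.

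Second, a reader might infer that the SAP results will flatter the drug. That is not established. The sign depends on the score course and the missingness, neither of which the documents give. With a flat course the rule was within 0.08 points of the truth, and censoring at last contact limits how far values travel. Nor can the summaries be called less powerful, because no hypothesis is tested and no power is stated.

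Third, the reach of the rule is uncertain. For r and s the SAP refers to latest available data, but the wording for h, l and t-z could be read as actual measurements only. That is fair, and it is a reason to settle the text.

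Fourth, the model has limits. It relies on data missing at random, which may fail if charts record scores more often in active disease. A Gaussian model suits 0-3 sub-scores poorly, and week-52 data may be thin. These points shape the fix but do not remove the need for one.

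**Conclusion.** The point holds as an undeclared departure on secondary outcomes, joined to an internal contradiction on imputation. It should be corrected before analysis, and protocol section 8.7 does not require an amendment for it. Under the stated carry-forward rule, stale values can be presented as week-52 change, in data the protocol itself expects to be incomplete.

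The size is not fixed by the documents. Under the assumed scenarios, week-52 bias ran from −0.22 to +0.39 points for the SAP rule and from −0.07 to +0.03 for the longitudinal model. These figures show that the direction is open and that the model is less sensitive to the course of disease. They do not predict this study's error, and they rest on a continuous score with missing visits unrelated to the score.

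**What to change.** In SAP section 7.2:

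1. Add the longitudinal model for the continuous outcomes: partial and full Mayo scores, f-calpro and CRP on the log scale, and the other laboratory values. Fit it to values observed within a stated window around weeks 8, 16, 24 and 52, with categorical time, the baseline value and within-patient correlation. Report estimated change with 95% CI and state the missing-at-random assumption. The protocol leaves these details open, so the SAP must set them. Four visits give 4 × 5 / 2 = 10 covariance parameters if unstructured, so name a simpler fallback in case week 52 is sparse.
2. For the 0-3 sub-scores (r and s), use observed-value summaries or an ordinal model.
3. Report observed-value delta summaries with the number actually measured per outcome and week, shown as fewer than 5 where the export rule in protocol section 8.6 applies.
4. Reconcile SAP section 6 with section 7.1, and label any carried-forward result a sensitivity analysis.
5. Add a note in section 2.2, as for objectives b/c, c/e and q, recording and justifying any departure from the protocol's method that remains.

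The cost is SAP wording and modest programming, with no new data. The visible downside is fewer values at week 52, which is information the reader should have.

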#### 8.8. Quality Control

Medaffcon has an internal quality control (QC)/log documentation used for RWE studies. The document records general data QC (including for example measures for data and variable coverages, number of individuals and data rows, changes as function of time and checks for systematic gaps on data coverage and outliers in the data where appropriate). Additionally, all notes or data processing and definitions, especially any deviations from SAP, will be recorded and later reported. All analyses and data processing will be performed using R, a language and environment for statistical computing and graphics, in R-studio environment. All analysis scripts will be saved, and there is version control and external back-ups for the scripts. At the end of study, all scripts will be archived to assure analysis reproducibility, and plausible later audits (by client and/or from scientific publication side).

All study results will be discussed within Medaffcon and Pfizer teams, and any uncertainties will be further validated by clinical experts and/or wider team of Pfizer and/or Medaffcon RWE experts and Data Scientists where appropriate.

#### 8.9. Limitations of the Research Methods

The main strength of this study is the nation- and patient-wide coverage of the cohort. The study is expected to include all 21 health care districts in Finland. The data is also versatile as it is derived from the patient information systems in the hospital districts.

The main limitation of the study are its' retrospective nature and the expected number of observations (approximately 100-150 patients). Therefore, some sub-group or stratified analyses are not necessarily possible. It is also likely that the data is partially incomplete because of the variation between hospitals. All variables or sum variable components are not necessarily available from different electronical health records. To a citinib has been used in Finland for a rather short time so data for all endpoints at all timepoints may not be calculated/available. As in the registry studies in general the primary data source (hospital electronic health record [EHR]) in this study may be prone to potential human errors. Data is subject to gaps and human errors made by physicians entering data into the system.

#### 8.10. Other Aspects

Not applicable.

#### 9. PROTECTION OF HUMAN SUBJECTS

#### 9.1. Patient Information

This study involves data that exist in anonymized structured format and contain no patient personal information.

#### 9.2. Patient Consent

As this study involves anonymized structured data, which according to applicable legal requirements do not contain data subject to privacy laws, obtaining informed consent from patients by Pfizer is not required.

#### 9.3. Institutional Review Board (IRB)/Independent Ethics Committee (IEC)

No waiver was received as this is not applicable. Per the Act on Secondary Use of Health and Social Data 552/2019 (in Finnish: Laki sosiaali- ja terveystietojen toissijaisesta käytöstä), no institutional review board or independent ethics committee for this retrospective registry study is required.

#### 9.4. Ethical conduct of the study

Per the Act on Secondary Use of Health and Social Data 552/2019 (in Finnish: Laki sosiaalija terveystietojen toissijaisesta käytöstä), no ethical approval for this retrospective registry study is required. This study protocol will be evaluated and approved by the Finnish Health and Social Data Permit Authority Findata before any activities.

The study will be conducted in accordance with legal and regulatory requirements, as well as with scientific purpose, value and rigor and follow generally accepted research practices described in Guidelines for Good Pharmacoepidemiology Practices (GPP).

# 10. MANAGEMENT AND REPORTING OF ADVERSE EVENTS/ADVERSE REACTIONS

Secondary Data Collection Study Structured Data Analysis

This study involves data that exist as structured data by the time of study start or a combination of existing structured data and unstructured data, which will be converted to structured form during the implementation of the protocol solely by a computer using automated/algorithmic methods, such as natural language processing.

In these data sources, individual patient data are not retrieved or validated, and it is not possible to link (ie, identify a potential association between) a particular product and medical event for any individual. Thus, the minimum criteria for reporting an adverse event (AE) (ie, identifiable patient, identifiable reporter, a suspect product, and event) cannot be met.

#### 11. PLANS FOR DISSEMINATING AND COMMUNICATING STUDY RESULTS

The detailed results obtained from this study will be available upon publication. Research results from this study will be published in peer reviewed scientific journals and international scientific congresses. The Authorship of any publications resulting from this study will be determined based on the International Committee of Medical Journal Editors (ICMJE) Recommendations for the Conduct, Reporting, Editing and Publication of Scholarly Work in Medical Journals.

In the event of any prohibition or restriction imposed (eg, clinical hold) by an applicable competent authority in any area of the world, or if the party responsible for collecting data from the participant is aware of any new information which might influence the evaluation of the benefits and risks of a Pfizer product, Pfizer should be informed immediately.

1 AMENDMENTS FROM PREVIOUS VERSION(S)

NA

2 INTRODUCTION

[figure not shown]
2.1 STUDY DESIGN

The target population for this study is adult ulcerative colitis patients who were prescribed to facitinib. Estimated number of patients in this study is 100-150, with the aim of covering all ulcerative colitis patients in Finland treated with to facitinib. The main inclusion criteria are a diagnosis of ulcerative colitis (ICD-10: K51) between January 2010 and December 2021 and treatment with to facitinib. The main exclusion criteria are age under 18 years, use of to facitinib before national reimbursement decision on 01 March 2019 and history of panproctocolectomy, ileal pouch-anal anastomosis (IPAA) or ileostomy.

The data collected has been generated as part of standard clinical care, treatment, and follow-up of ulcerative colitis patients. In accordance with the Finnish Act on Secondary Use of Health and Social Data 552/2019 (in Finnish: Laki sosiaali- ja terveystietojen toissijaisesta käytöstä), health registry data can be processed in scientific studies without patient consent. The purpose of this act is to establish conditions for the effective and secure processing of, and access to, personal health and social data for certain secondary purposes, such as research and statistics, innovation and development, knowledge management, teaching and authority planning. Thus, the Secondary Act creates a clear legal basis for the use of such registered data for research and innovation related to, for example, the health and well-being of citizens, the prevention of disease and the development of new treatment methods. This relatively new legislation is also a welcome unification of the fragmented Finnish national rules regarding the use of healthcare and social welfare data. In addition, it takes into consideration current data protection requirements.

The data will be collected by data miners in all hospital districts across Finland and entered into an electronic data mining tool (eDMT) which will be designed for the study in collaboration with Finnish clinicians. The data will be used to investigate and describe the patient population, treatment strategies and disease development.

Figure 1. Study Timeline

FPFV= First patient first visit, LPLV= Last patient last visit.

Please note that dates are subject to change depending on how long permit process with Findata takes.

Study population

The study is a descriptive single cohort study. Patients must meet all of the following inclusion criteria to be eligible for inclusion in the study:

- 1. Xeljanz (tofacitinib) usage for ulcerative colitis.
- 2. Diagnosis of ulcerative colitis (ICD-10: K51.0, K51.1, K51.2, K51.3, K51.5, K51.8, K51.9) between January 2010 and December 2021 (incident or prevalent).

Patients will be excluded if:

- 1. Age <18 years at the start of tofacitinib use.
- 2. Use of tofacitinib before reimbursement (01 Mar 2019).
- 3. < 8 weeks of treatment with to facitinib at the start of data mining.
- 4. History of panproctocolectomy, IPAA or ileostomy.

The primary variable is the first recording (date) with tofacitinib for the treatment of ulcerative colitis (ICD-10: K51). Additional variables to be collected according to the list in Table 1.

Table 1. Variables Collected in This Study

Data source for all variables is the eDMT based on patient charts.

Variable	Role	Operational definition
Tofacitinib start date	Index Inclusion criteria 1 Exclusion criteria 2	First day on tofacitinib administration
Date of birth	Exclusion criteria 1 Primary objective 7.2.1.a	Age will be defined as of index date
History of bowel surgery	Exclusion criteria 4	Panproctocolectomy, IPAA or ileostomy
Gender	Primary objective 7.2.1.a	Male/female
Smoking status	Primary objective 7.2.1.a	Current/ex-smoker/non- smoker/unknown
BMI	Primary objective 7.2.1.a	Derived from weight and height
Weight	Primary objective 7.2.1.a	kg
Height	Primary objective 7.2.1.a	ст
Treating hospital	Primary objective 7.2.1.a	name of treating hospital
Mayo score	Primary objective 7.2.1.c Secondary objectives 7.3.1.b, 7.3.1.c, 7.3.1.d, 7.3.1.e, 7.3.1.f, 7.3.1.i, 7.3.1.j, 7.3.1.k, 7.3.1.l, 7.3.1.o, 7.3.1.p.	Sum of "endoscopic findings", "stool frequency", Doctors assessment of disease severity" and "rectal bleeding"
First UC diagnose	Primary objective 7.2.1.b Inclusion criteria 2	Date
Extent of colonic involvement	Primary objective 7.2.1.b	Montreal classification: E1, E2 or E3
Endoscopic findings	Primary objective 7.2.1.c and 7.2.1.e. Secondary objective 7.3.1.m	0-3 (mayo score component)

Variable	Role	Operational definition
Histological activity	Primary objective 7.2.1.e Secondary objective 7.3.1.n	Active disease (2) / inactive disease (1) /normal histology (0) / not determined
Clinician's assessment of disease severity	Primary objective 7.2.1.c	0-3 (mayo score component)
Stool frequency	Primary objective 7.2.1.c Secondary objectives 7.3.1.r	0-3 (mayo score component)
Rectal bleeding	Primary objective 7.2.1.c Secondary objective 7.3.1.s	0-3 (mayo score component)
Fecal calprotectin	Primary objective 7.2.1.d, Secondary objectives 7.3.1.g and 7.3.1.h.	mg/kg
Plasma CRP	Primary objective 7.2.1.d Secondary objective 7.3.1.t	mg/L
Blood hemoglobin	Primary objective 7.2.1.d, Secondary objective 7.3.1.u	g/L
Blood leukocytes	Primary objective 7.2.1.d Secondary objective 7.3.1.v	cells/L
Blood thrombocytes	Primary objective 7.2.1.d Secondary objective 7.3.1.w	cells/L
Blood lymphocytes	Primary objective 7.2.1.d Secondary objective 7.3.1.x	cells/L
Blood neutrophiles	Primary objective 7.2.1.d Secondary objective 7.3.1.y	cells/L
Plasma albumin	Primary objective 7.2.1.d Secondary objective 7.3.1.z	g/L
Tofacitinib dose	Secondary objectives 7.3.1.a, 7.3.1.aa and 7.3.1.bb	mg*times/per day or "not on treatment"
Colectomies	Secondary objective 7.3.1.cc	Date
Type of healthcare contact	Secondary objective 7.3.1.cc	outpatient visit, remote contact, emergency visit or hospitalization

Variable	Role	Operational definition
Prior IBD treatments	Secondary objective 7.3.2	Yes/no (For each treatment)
 corticosteroids 5-aminosalicylic acid (5-ASA) azathioprine 6-mercaptopurine methotrexate cyclosporine ustekinumab vedolizumab adalimumab infliximab golimumab 		
Concomitant medications o corticosteroids o 5-ASA	Secondary objective 7.3.1.q,	product & dose
Extraintestinal manifestations: arthralgia, arthritis, sacroiliitis, pyoderma gangrenosum, erythema nodosum, primary sclerosing cholangitis, uveitis, ankylosing spondylitis, aphthous stomatitis, psoriasis	CCI	Yes/no per pre-specified list
Prior diagnoses	CCI	Yes/no per pre-specified list
Death date or lost to follow up	Used to define end of follow up	Date

Further operational definitions from the collected data include:

Active disease:

• An endoscopic Mayo sub-score of ≥ 2 or fecal-calprotectin (f-calpro) > 250 mg/kg.

Clinical response:

• A full Mayo score decrease of ≥ 3 points and a decrease of $\geq 30\%$ from baseline, with a decrease of ≥ 1 point on the rectal bleeding subscore or an absolute rectal bleeding score of ≤ 1 .

• A partial Mayo score (ie, Mayo score without endoscopic assessment) decrease of ≥2 points and reduction of at least 25% in partial Mayo (pMayo) score from baseline with an accompanying decrease in rectal bleeding sub score of ≥1 point or absolute rectal bleeding sub score of ≤1.

Clinical remission:

- A full Mayo score of ≤ 2 points with no individual sub score exceeding 1 point, with rectal bleeding sub-score of 0.
- A pMayo score < 2 points with rectal bleeding sub-score of 0.

Data source

This study relies on a secondary use of existing and available data in patient registers and patient charts in Finland. The data will be gathered from hospital patient information systems. All data in this study is collected from these patient information systems and made available in aggregated form for data-analysis.

